## **12.6 Handling of Missing Data**

No imputation of missing data is planned.

## **12.7 Safety Analyses**

The safety analysis set will include all eyes for which refractive surgery is attempted with test device (regardless of success or failure). All adverse events occurring from the time a subject signs informed consent to study exit will be accounted for in the reporting. Safety analyses will be conducted using the SAF through descriptive summaries (counts and percentages) and listings. In addition, separate subject listings will be provided for AEs that occur prior to refractive surgery using the test device.

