Assessment(s)	
Effectiveness
  

Manifest refraction

 
Safety
 

Patient reported outcome

Best corrected photopic distance visual acuity (BCDVA)

Manifest refraction

Intraocular pressure (IOP)

Slit lamp examination

Dilated fundus examination

 
Study Design	
This is a prospective, single-arm, multi-center, interventional study with planned bilateral treatment.
 
Qualified subjects will receive bilateral LASIK treatment and be followed for 1 year. Subjects will be asked to attend a total of 9 visits (screening, surgery, day 1, 1 week, 1 month, 3 month, 6 month, 9 month, and 1 year). Total expected duration of subject participation is approximately 1 year.

Subject population	
Subjects 18 years of age or older who desire to have LASIK will be consented and screened for meeting the inclusion and exclusion criteria.
 
Planned number of subjects enrolled/consented: approximately 70 eyes (35 subjects)
 
Planned number of treated/randomized subjects: approximately 60 eyes (30 subjects)

	
Planned number of completed subjects: approximately 50 eyes (25 subjects)

Key inclusion criteria  (See Section 8.1 for a complete list of inclusion criteria)	
Subjects must meet all inclusion criteria as listed in Section 8.1.
 
Key Inclusion Criteria include:
 

• Hyperopia up to +3.0 D of sphere with and without astigmatic refractive error up to +3.0 D at the spectacle plane, with a maximum MRSE of +3.0 D

• Intended to treat bilaterally

• Best corrected photopic distance visual acuity of 20/20 or better

• Uncorrected photopic distance visual acuity of 20/40 or worse

• Stable refraction (within <math>\pm 0.50</math> D), as determined by MRSE for a minimum of 12 months prior to surgery

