### **10.2.2 Adverse Event Collection: Safety Assessment**

All Study Visits

Assess and record any adverse events that are observed or reported, including those associated with changes in concomitant medication dosing since the previous visit.

*Note:* AEs and device deficiencies must be recorded for all enrolled subjects from the time of signature of informed consent until their exit from the study, regardless of subject enrollment status (screen failure or received treatment).

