### **Specific Events Relevant to this Protocol**

In addition to reporting all AEs (serious and non-serious) meeting the definitions, the Investigator must report any occurrence of the following as an ocular SAE:

- Diffuse lamellar keratitis (Grade 3 or above)
- Corneal infiltrate or ulcer

- Any persistent corneal epithelial defect at one month or later
- Corneal edema at 1 month or later (specify flap or bed)
- Epithelium in the interface with loss of 2 lines (10 letters) or more BCDVA
- Miscreated flap (lost, incomplete, too thin)
- Melting of the flap
- IOP with increase of > 10 mmHg above baseline on two consecutive examinations or an IOP greater than 30 mmHg on two consecutive examinations
- Haze beyond 6 months with loss of 2 lines or greater ( $\geq$  10 letters ETDRS) of BCDVA
- Decrease in BCDVA of greater than or equal to 2 lines ( $\geq$  10 letters ETDRS) not due to irregular astigmatism as shown by rigid contact lens refraction at 3 months or later
- Retinal detachment
- Retinal vascular accidents
- Ocular penetration
- Any other vision-threatening event

The Investigator must also report the following ocular AEs:

- Diffuse lamellar keratitis (Grade 2 or less)
- Corneal edema between one week and 1 month after the procedure
- Peripheral corneal epithelial defect at 1 month or later (location of the defect to be identified as on, off, or across the flap)
- Epithelium in the interface
- Foreign body sensation at 1 month or later
- Pain at 1 month or later
- Ghost/double images in the operative eye
- Flap is not of the size and shape as initially intended or resultant flap is misaligned

AEs that occur in association with a device that is used in conjunction with FS200 will be reported separately from those occurring with EX500.

This list is consistent with the categories provided in ANSI Z80.11 2012(R2017). Any other potentially sight-threatening event may also be considered serious based on the judgment of the Investigator and should be reported appropriately as delineated in Section 11.3.

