## 11.6 Follow-Up of Subjects with Adverse Events

The Investigator is responsible for adequate and safe medical care of subjects during the study and for ensuring that appropriate medical care and relevant follow-up procedures are maintained after the study.

The Investigator should provide the Study Sponsor with any new safety information (which includes new AEs and changes to previously reported AEs) that may affect the safety evaluation of the device. For AEs that are unresolved/ ongoing at time of subject exit from study, any additional information received at follow-up should be documented in the eCRFs up to study completion (ie, database lock).

Any additional data received up to 6 months after subject discontinuation or exit must be documented and available upon the Study Sponsor's request. All complaints received after this time period will be considered and processed as spontaneous (following the postmarket vigilance procedures) and should be communicated to the medical device's manufacturer as per local requirements.

The Investigator should also report complaints on non-Alcon products directly to the manufacturer as per the manufacturer's instructions or local regulatory requirements.

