### **12.7.1 Analysis of Primary Safety Endpoint(s)**

In order to assess safety of the WaveLight EX500 excimer laser system for the correction of hyperopia with and without astigmatism, the following primary safety endpoint is defined:

- Percentage of eyes experiencing ocular adverse events

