#### **12.7.1.2 Analysis Methods**

The SAF will be used for this analysis. The number and percentage of eyes experiencing each of the primary safety endpoints will also be calculated.

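### The primary safety percentage counts ocular AEs only up to each subject's exit but divides by every eye in the safety set, so read as a 1-year risk it is modestly too low

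*Protocol*

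**What the plan says.** The numerator closes at each subject's own exit. Protocol 12.7 says: "All adverse events occurring from the time a subject signs informed consent to study exit will be accounted for in the reporting". Protocol 10.2.2 collects AEs over the same period, "from the time of signature of informed consent until their exit from the study".

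The endpoint in Protocol 12.7.1 is "Percentage of eyes experiencing ocular adverse events", with no time horizon. For the denominator, Protocol 12.7.1.2 says "The SAF will be used for this analysis". The SAF (Protocol 12.2.1, SAP 2.2) is all eyes with attempted surgery, whether or not they are followed. SAP 5.3.1 gives counts and percentages without a window, a denominator or a rule for early exits. Protocol 12.6 plans no imputation, and Protocol 12.7.1.1 and SAP 5.2 plan no safety hypothesis.

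Protocol 7.1 says subjects are followed for at least 12 months (Day 330 to 420) for safety. On attrition, Protocol 8 expects up to 10% loss to follow-up. The Protocol Summary plans about 60 treated eyes and gives "Planned number of completed subjects: approximately 50 eyes (25 subjects").

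**The concern.** Eyes with unequal follow-up enter one crude percentage with equal weight. An eye with no AE by an early exit counts the same as an eye with no AE after a full year. For a 1-year risk, this can only pull the figure below what full follow-up of the same eyes would have shown.

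Some events listed in Protocol 11.1 are defined by time: corneal edema, pain and persistent epithelial defect at 1 month or later, BCDVA loss at 3 months or later, and "Haze beyond 6 months with loss of 2 lines or greater" of BCDVA. Protocol 11.3 adds dry eye and visual disturbances, whose AE status can turn on whether they persist past 6 months. An eye that exits before such a period opens cannot contribute that particular event but stays in its denominator.

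The trial has one arm, so no control group shares the bias. This percentage is the only primary safety endpoint in a study meant to support registration in Japan.

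**Working it through.** **Inputs from the documents.** About 35 subjects consented, 30 treated (60 eyes) and 25 completing (50 eyes), with 10% screen failure and up to 10% loss (Protocol 3 and 8).

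**Assumptions.** The documents give no ocular AE rate and no exit times. I take a true 1-year risk p of 5% to 30%, the same in lost eyes as in retained eyes.

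**Step 1: the plan's own attrition.** 25/0.9 = 27.8, so 28 treated against 30 stated. 30/0.9 = 33.3, so 34 consented against 35 stated. The figures reproduce with some rounding up. Two readings of the loss follow:

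- Stated rate: 10% of 60 = 6 eyes, d = 0.10.
- Treated minus completed: 60 − 50 = 10 eyes, d = 10/60 = 0.167.

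**Step 2: expected crude percentage.** Let F be the share of a lost eye's 1-year risk that falls before its exit. Then

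expected percentage = p × [1 − d(1 − F)].

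The floor is F = 0: none of the lost eyes' risk is observed. At p = 10% this gives 10% × 0.90 = 9.0% (6 lost) or 10% × 0.833 = 8.3% (10 lost).

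**Step 3: constant hazard, exits uniform over the year.** With λ = −ln(1 − p), a lost eye shows an event before exit with probability 1 − p/λ. At p = 10%, λ = 0.1054 and this is 1 − 0.1/0.1054 = 0.051.

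- 6 lost: 0.90 × 10% + 0.10 × 5.1% = 9.5%.
- 10 lost: 0.833 × 10% + 0.167 × 5.1% = 9.2%.

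| Assumed 1-year risk | Uniform exit, 6 lost | Uniform exit, 10 lost | Floor, 6 lost | Floor, 10 lost |
|---|---|---|---|---|
| 5% | 4.8% | 4.6% | 4.5% | 4.2% |
| 10% | 9.5% | 9.2% | 9.0% | 8.3% |
| 20% | 19.0% | 18.4% | 18.0% | 16.7% |
| 30% | 28.6% | 27.6% | 27.0% | 25.0% |

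The relative shortfall is about 5% or 8% under uniform exits and at most 10% or 16.7%. If 80% of the risk falls before exit (F = 0.8), it is 2% or 3.3%. At p = 10%, uniform exits miss 0.3 to 0.5 eye of 60 and the floor misses 0.6 to 1.0 eye. The largest case in the table (p = 30%, 10 lost, floor) misses 3 eyes.

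**Step 4: scale.** The exact 95% interval for 6/60, treating eyes as independent, is 3.8% to 20.5%. That is much wider than the shift, although an interval does not reflect a bias that runs in one direction.

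**The case against.** The strongest reply is that nothing is misstated. The endpoint names no horizon, and as the percentage of treated eyes with an ocular AE on study it is correct. No hypothesis or target depends on it, and the likely shift is an eye or less at a 10% risk. This stands, and it is why the SAF percentage should stay. It does not remove the need to label the figure, because Protocol 7.1 sets at least 12 months of safety follow-up and a reader will naturally take it as a 1-year figure.

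A reader might go further on several points where the documents give no support:

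- *Early-exit eyes cannot be cases.* The endpoint is any ocular AE. Protocol 11.1 includes events with no time qualifier and events before 1 month. The Early Exit visit covers AEs, slit lamp, BCDVA, IOP and fundus if the subject is willing and able (Table 3-1, Protocol 10.4.3). Only specific late categories are out of reach.
- *Section 11.6 already gathers post-exit events, and 12.7 discards them.* Section 11.6 asks for "any new safety information (which includes new AEs and changes to previously reported AEs") and says "Any additional data received up to 6 months after subject discontinuation or exit must be documented". It sets no post-exit visit or active contact, and its eCRF instruction concerns AEs already ongoing at exit. Adding such reports to the numerator would mix passive with active ascertainment.
- *The percentage among eyes with Visit 7 is the remedy.* It drops early-exit eyes that had events. If 2 of 6 event eyes were among 10 lost, it would give 4/50 = 8.0% against 6/60 = 10.0%.

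SAP 5.3.11 to 5.3.13 also summarise IOP, slit lamp and fundus findings by visit. The public text omits some safety subsections, so related summaries may exist there. The point is confined to the readable text of Protocol 12.7 and SAP 5.3.1.

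**Conclusion.** The point holds as a modest downward bias in the primary safety percentage when it is read as a 1-year risk. With 6 to 10 of 60 eyes lost and an assumed 10% risk, the expected figure is about 9.5% to 9.2%, with a floor of 9.0% to 8.3%. These values rest on assumed AE rates and exit times, and on lost eyes having the same risk as the others.

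A reader might infer a much larger gap, up to 10/60 = 16.7 percentage points. That would need an uncounted ocular AE in every one of 10 lost eyes, and nothing in the documents points to it. Nor do they show that subjects with poor outcomes would leave unrecorded, since an AE found at or before the Early Exit visit counts.

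**What to change.** In Protocol 12.7 and SAP 5.3.1:

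1. Keep the SAF percentage and state that it is the percentage of eyes with an ocular AE observed on study, up to each subject's exit.
2. Add a Kaplan-Meier 1-year cumulative percentage of eyes with an ocular AE, censored at exit, with a confidence interval that allows for two eyes per subject. Name the day at which the curve is read, since Visit 7 spans Day 330 to 420. The estimate assumes that exit is unrelated to later AE risk, and the SAP should say so.
3. Report time-qualified events (1 month or later, 3 months or later, beyond 6 months) over the eyes examined at or after that time.
4. List any post-exit AEs received under Protocol 11.6 separately, outside the numerator.

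The cost is some wording, one or two table columns and a short listing, with no new visits or data collection. The 1-year figure may look slightly less favourable than the crude one.

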### **12.7.1 Analysis of Primary Safety Endpoint(s)**

In order to assess safety of the WaveLight EX500 excimer laser system for the correction of hyperopia with and without astigmatism, the following primary safety endpoint is defined:

- Percentage of eyes experiencing ocular adverse events

#### **12.7.1.1 Statistical Hypotheses**

No hypothesis testing of the primary safety endpoints is planned.

#### **12.7.1.2 Analysis Methods**

The SAF will be used for this analysis. The number and percentage of eyes experiencing each of the primary safety endpoints will also be calculated.

## 13 DATA HANDLING AND ADMINISTRATIVE REQUIREMENTS

### 13.1 Subject Confidentiality

The Investigator must ensure that the subject's anonymity is maintained throughout the course of the study. In particular, the Investigator must keep an enrollment log with confidential identifying information that corresponds to the subject numbers and initials of each study participant. At the end of the clinical study, the Study Sponsor will collect a copy of the enrollment log **without any identifying subject information**. All documents submitted to the Study Sponsor will identify the subjects exclusively by number and demographic information. No other personally identifying information will be transmitted to the Study Sponsor.

The Study Sponsor may release anonymized study data to external researchers for purposes of future research directly related to the study objectives, or future research that is beyond the scope of the current study objectives. The Informed Consent Form explains this to study subjects. Anonymization means that all identifiable information will be removed from the dataset and all links to the subjects in the study will be removed. Anonymization of the data will maintain confidentiality of the subjects who participate in the study so that they cannot be identified by external researchers. The anonymized data set will contain records from all of the subjects in the current study, but the anonymization process might change the data set in some ways, so external researchers will be informed that they might not be able to duplicate some of the results from this study.

### 13.2 Completion of Source Documents and Case Report Forms

The nature and location of all source documents will be identified to ensure that original data required to complete the CRFs exist and are accessible for verification by the site monitor, and all discrepancies shall be appropriately documented via the query resolution process. Site monitors are appointed by the Study Sponsor and are independent of study site staff.

If electronic records are maintained, the method of verification must be determined in advance of starting the study.

At a minimum, source documents include the following information for each subject:

- Subject identification (name, sex, race/ethnicity)
- Documentation of subject eligibility
- Date of informed consent

- Dates of visits
- Documentation that protocol specific procedures were performed
- Results of study parameters, as required by the protocol
- IP accountability records
- Documentation of AEs and other safety parameters (if applicable)
- Records regarding medical histories and the use of concomitant therapies prior to and during the study
- Date of study completion and reason for early discontinuation, if applicable

It is required that the author of an entry in the source documents be identifiable. Direct access to source documentation (medical records) must be allowed for the purpose of verifying that the data recorded on the CRF are consistent with the original source data.

Only designated individuals at the site will complete the CRFs. The CRFs must be completed at regular intervals following the clinical study visit schedule. It is expected that all data reported have corresponding entries in the source documents. The Principal Investigator is responsible for reviewing and certifying that the CRFs are accurate and complete. The only subject identifiers recorded on the CRFs will be subject number, and subject demographic information.

### **13.3 Data Review and Clarifications**

A review of CRF data to the subject's source data will be completed by the site monitor to ensure completeness and accuracy. After the CRFs have been completed, additional data clarifications and/or additions may be needed as a result of the data cleaning process. Data clarifications are documented and are part of each subject's CRF.

### **13.4 Sponsor and Monitoring Responsibilities**

The Study Sponsor will designate a monitor to conduct the appropriate site visits at the appropriate intervals according to the study monitoring plan. The clinical investigation will be monitored to ensure that the rights and well-being of the subjects are protected, the reported data are accurate, complete, and verifiable from the source documents, and the study is conducted in compliance with the current approved protocol (and amendments[s], if applicable), with current GCP, and with applicable regulatory requirements.

The site may not screen subjects or perform the informed consent process on any subject until it receives a notification from an appropriate Study Sponsor representative that the site may

commence conducting study activities. Monitoring will be conducted periodically while the clinical study is ongoing. Monitoring methods may include site visits, telephone, written and email correspondence. Close-out visits will take place after the last visit of the last subject at the site.

A Coordinating Investigator may be identified by the Study Sponsor to review and endorse the final study report. In cases where a Coordinating Investigator is engaged, the Study Sponsor will select the Coordinating Investigator based upon their experience, qualifications, active study participation, and their willingness and availability to take on this role.

Additionally, Alcon may have an expert Sponsor Observer or Representative present during screening or surgery to offer training to the Investigator on proper operation of the device and/ or to make technical observations during the study visit.

- The Sponsor Representative must be supervised by the Investigator or designee to ensure the Sponsor Representative's presence or activities do not bias the outcome of the study, affect the quality of the research data, and/or compromise the rights and welfare of the subject. The Sponsor Representative will not intervene with the standard of care provided to study subjects or make safety-related decisions or assessments. The activities of Sponsor Representatives will be described in the Informed Consent.

### **13.5 Regulatory Documentation and Records Retention**

The Investigator is required to maintain up-to-date, complete regulatory documentation as indicated by the Study Sponsor and the Investigator's files will be reviewed as part of the ongoing study monitoring. Financial information is to be kept separately.

Additionally, the Investigator must keep study records and source documents consistent with the terms of the clinical study agreement with the Study Sponsor. If the Investigator retires, relocates, or for any other reason withdraws from responsibility of keeping the study records, then the Study Sponsor must be notified and suitable arrangements made for retention of study records and source documents needed to comply with national and international regulations.

### **13.6 Quality Assurance and Quality Control**

The Study Sponsor will secure agreement from all involved parties to ensure direct access to all study related sites, source data and documents, and reports for the purpose of monitoring and auditing by the Study Sponsor, and inspection by domestic and foreign regulatory

authorities. Quality control will be applied to each stage of data handling to ensure that all data are reliable and have been processed correctly. Agreements made by the Study Sponsor with the Investigator/Institution and any other parties involved in the clinical study will be provided in writing as part of the protocol or as a separate agreement.

## 14 ETHICS

This clinical study must be conducted in accordance with the ethical principles contained within:

- The Declaration of Helsinki, and in compliance with the ICH E6 GCP Consolidated Guideline, ISO 14155:2011, and the applicable US FDA 21 CFR Regulations.
- SOPs of the Study Sponsor and contract research organizations participating in the conduct of the clinical study and all other applicable regulations.
- Notifications and timelines for reporting protocol deviations should be based upon applicable Ethics Committee requirements

The Investigator must ensure that all personnel involved in the conduct of the study are qualified to perform their assigned responsibilities through relevant education, training, and experience. The Investigator and all clinical study staff must conduct the clinical study in compliance with the protocol. Deviations from this protocol, regulatory requirements and/or GCP must be recorded and reported to the Sponsor prior to database lock. If needed, corrective and preventive action should be identified, implemented, and documented within the study records. Use of waivers to deviate from the clinical protocol is prohibited.

Before clinical study initiation, this protocol, the informed consent form, any other written information given to subjects, and any advertisements planned for subject recruitment must be approved by an IRB/IEC. The Investigator must provide documentation of the IRB/IEC approval to the Study Sponsor. The approval must be dated and must identify the applicable protocol, amendments (if any), informed consent form, assent form (if any), all applicable recruiting materials, written information for subject, and subject compensation programs. The IRB/IEC must be provided with a copy of the User Manual, any periodic safety updates, and all other information as required by local regulation and/or the IRB/IEC. At the end of the study, the Investigator must notify the IRB/IEC about the study's completion. The IRB/IEC also must be notified if the study is terminated prematurely. Finally, the Investigator must report to the IRB/IEC on the progress of the study at intervals stipulated by the IRB/IEC.

Voluntary informed consent must be obtained in writing from every subject and the process shall be documented before any procedure specific to the clinical investigation is applied to

the subject. The Investigator must have a defined process for obtaining consent. Specifically, the Investigator, or their delegate, must explain the clinical study to each potential subject and the subject must indicate voluntary consent by signing and dating the approved informed consent form. The subject must be provided an opportunity to ask questions of the Investigator, and if required by local regulation, other qualified personnel. The Investigator must provide the subject with a copy of the consent form written in a language the subject understands. The consent document must meet all applicable local laws and provide subjects with information regarding the purpose, procedures, requirements, and restrictions of the study, along with any known risks and potential benefits associated with the IP and the study, the available compensation, and the established provisions for maintaining confidentiality of personal, protected health information. Subjects will be told about the voluntary nature of participation in the study and must be provided with contact information for the appropriate individuals should questions or concerns arise during the study. The subject also must be told that their records may be accessed by appropriate authorities and Sponsor-designated personnel. The Investigator must keep the original, signed copy of the consent (file in subject's medical records) and must provide a duplicate copy to each subject according to local regulations.

The Study Sponsor assures that the key design elements of this protocol will be registered on [www.clinicaltrials.gov](http://www.clinicaltrials.gov) as required by current regulations and, if applicable, other public databases as required by local country regulations. In addition, results of this study will be made publicly available on [www.clinicaltrials.gov](http://www.clinicaltrials.gov) regardless of outcome as required by current regulations and, if applicable, in other public databases as required by local country regulations.

